### **Stratification**

Stratified randomization will be performed based on two a priori factors that can influence outcome: unilateral vs. bilateral reconstruction, and study site. (Study Schema diagram) It is well documented in the literature that aesthetic outcomes tend to be superior in bilateral reconstructions than unilateral cases. In addition, patients will be stratified by the study site as there may be significant differences in patient characteristics for each individual hospital catchment area.

### **9b. Intention to treat analysis**

Patients who abandon reconstruction or undergo premature explanation of either TE or implant will **not** be removed from the study and will be evaluated using the **intention-to-treat analysis**.

### **9c. Measurement of the Primary Objective:**

#### ***i) Primary Analysis***

Each of the two domain-specific summary scores on function and satisfaction will be transformed on a scale from 0 to 100 using RUMM software. Mean scores and standard deviation for each surgery group will be calculated and compared. To address our primary aim of comparing patient satisfaction and quality of life between **Group 1** (one-stage with ADM) and **Group 2** (two-stage group without ADM) before and at the three post mastectomy follow up reference time points, we will use the **repeated measure analysis** to examine the time effect and time-group interaction. In all analyses, statistical significance will be designated at  $p <= 0.05$  level.

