#### **iib-7. Confounders and their Measurements**

Critical covariates will be identified at baseline and documented in the demographic assessment forms. These confounders can be conceptually divided into procedure specific, patient specific, and disease specific confounders. Analysis will be adjusted for the confounders using both stratification and multivariate regression. (see section on Outcome and their measurements) Stratified randomization is

performed based on laterality of the reconstruction (unilateral vs. bilateral) and study site. Other procedure specific confounders include skin-sparing vs. nipple-sparing mastectomy and the primary reconstructive surgeon. The patient specific confounders will include age, body mass index; socioeconomic status assessed using proxy measures of income and highest obtained level of education and marital status. Co-morbidities will be categorized as having one or more the following possible chronic conditions (emphysema, heart disease, diabetes, hypertension, stroke, arthritis, or other chronic condition). The disease specific confounders will include stage of breast cancer and present or past chemotherapy treatment.

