## **iib-8. Outcomes and their measurements**

### **Primary Outcome: *Patient-Reported Satisfaction and Quality of Life***

Patient satisfaction and quality of life will be measured using the Breast Q $\circ$  as a self-administered questionnaire. The Breast Q $\circ$  has 2 subscales that examine the two different domains: satisfaction and psychosocial function. The scores generated for each subscale will be transformed on a scale from 0-100, lowest to highest summary scores respectively. Scale validity and reliability are supported by the high Cronbach's alpha coefficient (>0.80) and intra-class correlation coefficients (>0.70). The scores generated for each subscale will be transformed on a scale from 0-100, lowest to highest summary scores respectively. Participants will be asked to complete the pre-operative module of the Breast Q $\circ$  questionnaire at 2 weeks prior to the mastectomy.(APPENDIX 4) Post-operatively, they will be requested to complete the post-operative module of the Breast Q $\circ$  at 2 weeks following immediate reconstruction, as well as 6 months and 1 year following the completion of the reconstruction. (APPENDIX 5) The questionnaires will be self-administered and mailed to the participants with return envelopes and prepaid postage. To compensate our study patients for their participation, a monetary reimbursement (\$10) will be available upon completion. The Dillman method will be used to encourage patient response.

The **secondary outcomes** will include a comparison of:

1. **short and long-term complication rates**: Short-term complications are intra- and post-operative complications occurring within two months of surgery and long-term complications occur later than two-months. They will be documented and collected prospectively.

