## **iib-9. Data Analysis**

### **9a. Confounders and their Measurements**

Critical covariates will be identified at baseline and documented in the demographic assessment forms. (APPENDIX 7) Analysis will be adjusted for the confounders using both stratification and controlled for during repeated measures analysis using SPSS v18.

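### The primary Breast Q analysis makes the pre-operative module the first level of the repeated outcome instead of a covariate, so the time effect spans two modules and the arm comparison is unbiased but inefficient.

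*Combined protocol and SAP*

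**What the plan says.** Section iib-8 uses one form of the Breast Q before surgery and another after it. For the first, two weeks before mastectomy: "Participants will be asked to complete the pre-operative module of the Breast Q" (Appendix 4). After surgery, "they will be requested to complete the post-operative module of the Breast Q" (Appendix 5), at two weeks after immediate reconstruction "as well as 6 months and 1 year following the completion of the reconstruction".

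Section 9c, i) says that each of the two domain scores "will be transformed on a scale from 0 to 100 using RUMM software". It then compares the two groups "before and at the three post mastectomy follow up reference time points", by a repeated-measures analysis whose stated purpose is "to examine the time effect and time-group interaction". The outcome therefore has four time levels, the first from the pre-operative module. No baseline-adjusted contrast between groups is named.

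Section 9a says that covariates are "controlled for during repeated measures analysis using SPSS v18". The list in section iib-7 covers procedure, patient and disease factors (for example, "The patient specific confounders will include age, body mass index"). The pre-operative Breast Q score is not on it.

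**The concern.** Two consequences follow from treating the pre-operative score as a level of the outcome.

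First, the step from the first to the second level of the time effect is also a step from one module to the other. A common 0 to 100 range is not by itself a common metric, and nothing in the documents says that the modules share one. One of the two named effects therefore rests on an unstated assumption.

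Second, the interaction is the only named model effect that can show a difference between arms. The hypothesis in section i is a benefit at all three follow-ups. If that benefit is roughly constant, and randomised arms start level, the interaction sees it only as a contrast with the pre-operative score and so carries that score's noise. It also spreads one question over three degrees of freedom. The plan collects a baseline that could sharpen the arm comparison but does not use it in that way.

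**Working it through.** **Inputs.** From section iib-10: 72 per arm, SD 20, difference 10, alpha 0.05 (taken as two-sided). Not in the documents, hence assumed: the correlation r between the pre-operative score and each follow-up score (0.2 to 0.5 shown), and the correlation p between follow-up scores (0.5 and 0.7 shown).

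**The plan's own figure.** n per arm = 2 × (1.960 + 1.036)² × 20² / 10² = 71.8, so 72. This reproduces the plan's number at 85% power. It is a two-group comparison of means at one occasion and uses no baseline score.

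**Constant 10-point benefit at all three follow-ups.** All noncentrality parameters contain (72/2) × 10²/20² = 9.

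- Four-level interaction (multivariate, F on 3 and 140 df): 9 / [(1+2p)/3 + 1 − 2r].
- Average of the three follow-ups, no baseline (F on 1 and 142 df): 9 / [(1+2p)/3].
- Average of the three follow-ups, baseline as covariate (F on 1 and 141 df): 9 / [(1+2p)/3 − r²].

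Example with p = 0.5 and r = 0.2: the interaction has 9 / (0.667 + 1 − 0.4) = 7.11. The unadjusted average has 9 / 0.667 = 13.5. The adjusted average has 9 / (0.667 − 0.04) = 14.36.

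| Power, % | r = 0.2 | 0.3 | 0.4 | 0.5 |
|---|---|---|---|---|
| p = 0.5: four-level interaction | 58.3 | 66.6 | 76.6 | 87.4 |
| p = 0.5: average, no baseline | 95.4 | 95.4 | 95.4 | 95.4 |
| p = 0.5: average, baseline as covariate | 96.4 | 97.5 | 98.7 | 99.6 |
| p = 0.7: four-level interaction | 53.7 | 60.9 | 69.8 | 80.1 |
| p = 0.7: average, no baseline | 91.5 | 91.5 | 91.5 | 91.5 |
| p = 0.7: average, baseline as covariate | 92.8 | 94.2 | 96.1 | 98.0 |

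**Where the gain comes from.** At p = 0.5 and r = 0.2, moving to the averaged group effect supplies 95.4 − 58.3 = 37.1 of the 38.1 points gained. At r = 0.5 it supplies 8.0 of 12.2. The covariate supplies the rest. In variance terms the covariate removes r² / [(1+2p)/3] of the variance of the average: 6% to 37.5% at p = 0.5, and 5% to 31% at p = 0.7.

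**Like-for-like check.** A 3-df test on the three follow-ups that ignores baseline has 87.4% (p = 0.5) or 80.1% (p = 0.7). Its noncentrality is 9 / [(1+2p)/3], which equals that of the interaction when 1 − 2r = 0. Against that test the planned use of baseline loses power below r = 0.5, breaks even at 0.5 and gains above it (96.6% at r = 0.6, p = 0.5).

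**Benefit at one visit only (10 points, p = 0.5).** The interaction has 85.4% to 87.4% over r = 0.2 to 0.5, against 87.4% for the post-only 3-df test, so little is lost. The adjusted average has only 24% to 34% here.

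**Form of the test.** If the interaction is instead tested in the univariate way under compound symmetry (all correlations equal to r, F on 3 and 426 df), its power is 68/74/81/88% at r = 0.2/0.3/0.4/0.5, still below the adjusted average.

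**Dropping baseline but keeping the interaction.** A constant benefit then leaves no interaction to detect, and power is 5%. The test has to change as well as the outcome vector.

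**The case against.** The case for the plan has real weight.

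- A reader might infer that the two modules measure different things, natural breasts before and a reconstruction after, so that the time effect cannot be read as change. The documents do not show this. The appendices are not reproduced, both domains are scored to 0 to 100, and a difference in what is rated would not obviously extend to the psychosocial domain. What stands is that comparability is relied on without being stated.
- A reader might infer that the treatment comparison is biased. It is not biased by the change of module: a shift common to both arms cancels from the interaction, and no hypothesis in section i rests on the time effect pooled over arms.
- Section 9c also says that group means and standard deviations will be compared, which fits the sample-size calculation and needs no baseline. But that sentence names no visit, test or use of baseline, and the repeated-measures analysis is the one tied to the primary aim.
- The model is left open. One that constrains the arms to equal baseline means would largely remove the power loss, but the text does not specify it.

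**Conclusion.** The point holds as a matter of efficiency and interpretation. The pre-operative module is a level of the outcome and is not a covariate. The time effect crosses modules without a stated common metric. Under a constant benefit, the named interaction has less power than a baseline-adjusted average of the follow-ups in every scenario computed: 58% to 87% against 96% to 99.6% at p = 0.5, and 54% to 80% against 93% to 98% at p = 0.7. These figures rest on assumed correlations, equal SDs of 20 and complete data.

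Three stronger readings are not supported. Using baseline as a level does not cost power in general: against a like-for-like test that ignores baseline it does so only for r below 0.5, and hardly at all if one visit alone differs. A low r is plausible with two modules and surgery in between, but that is an assumption. The trial also does not fall short of its stated 85%, because that figure describes a two-group comparison of means and was never claimed for the interaction. Finally, the near-certain power of the adjusted average should not be credited mainly to the covariate, since most of it comes from averaging three visits and testing a group effect.

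**What to change.** In section 9c, i):

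- Make the three post-operative-module scores the repeated outcome.
- Enter the pre-operative-module score of the same subscale as a covariate.
- Name the adjusted between-arm difference, averaged over the follow-ups, as the primary test in place of the time-by-group interaction, with adjusted estimates at each visit alongside it.
- Report the pre-operative score, and change from it, descriptively.
- Add the pre-operative score to the covariates in section iib-7.

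This needs only a change of wording and no new data. There are two costs. Change from before surgery is no longer formally tested. The average is also insensitive to a benefit confined to one visit. The stated hypothesis of benefit at all three follow-ups justifies the average, and the per-visit estimates guard against missing such a pattern.

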1. To compare patient satisfaction and QOL between one-stage ADM and two-stage TE/I reconstruction without ADM following mastectomy. Patient satisfaction will be evaluated using the Breast Q© at two-weeks, as well as six months and one year following completion of reconstruction.

**Hypothesis:** Patient satisfaction and QOL will be higher in the ADM assisted one-stage implant reconstruction group compared to the two-stage TE/I group at all three time-points.

The **secondary objectives** of this study are:

1. To compare the short- and long-term complication rates between the two techniques.

**Hypothesis:** The use of ADM in one-stage prosthetic breast reconstruction is not associated with increased short- and long-term postoperative complications compared with the traditional two staged TE/I procedure.

2. To examine the overall aesthetic outcome achieved using the ADM facilitated one-staged breast reconstruction at six months and one year following completion of the reconstruction.

**Hypothesis:** The overall aesthetic outcome achieved using the ADM facilitated one-stage breast reconstruction is superior to that following the two-stage breast reconstruction.

3. To perform a cost-effectiveness analysis (CEA) of the two reconstruction methods using the net benefit regression model on person-level cost and effect data collected during the study.

**Hypothesis:** Both the direct and indirect cost will be reduced and patient-reported utility will be greater for the one-stage ADM method compared to the TE/I method.

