### **iib-10. Sample Size**

We consider clinically relevant change in the quality of life as a difference that exceeds half a standard deviation of the baseline value. Field-testing data of the Breast Q $\odot$  has found that the standard deviation of both the psychosocial function and satisfaction distributions is approximately 20. Thus, the minimum significant difference of score in each subscale is calculated to be 10. When we set our power at 85% with a  $\beta$  error of 0.1 and a standard  $\alpha$  error rate of 0.05, and applied the equation for equal sample sizes, we calculated a **minimum sample size of 72 patients per arm** for a total sample size of 144 patients. This sample size is also sufficient with power 84%,  $\alpha$  0.05, to detect a value of 0.06 for  $\eta^2$ , representing a medium effect size of the proportion of variability in the outcome variable (Breast Q $\odot$ ) that is explained by the independent variable(s), e.g., intervention.

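### Two Breast Q subscales are each tested at 0.05 with no success rule; if either one suffices, the error rate is about 8-10%, not 5%

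*Combined protocol and SAP*

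**What the plan says.** Section iib-8 says that the Breast Q "has 2 subscales that examine the two different domains: satisfaction and psychosocial function". Section 9c i) keeps the two apart: "Each of the two domain-specific summary scores on function and satisfaction will be transformed" to a 0-100 scale. Group means and standard deviations are to be compared, and a repeated measures analysis is to examine the effect of time and its interaction with group, "before and at the three post mastectomy follow up reference time points". One threshold covers everything: "In all analyses, statistical significance will be designated at" p <= 0.05.

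The Specific Aims hypothesise that satisfaction and quality of life will be higher with one-stage ADM "compared to the two-stage TE/I group at all three time-points".

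Section iib-10 treats the subscales one at a time: "the minimum significant difference of score in each subscale is calculated to be 10", from a standard deviation of about 20 for both. It uses an "error rate of 0.05, and applied the equation for equal sample sizes", arriving at 72 per arm.

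None of these sections names a lead subscale, a primary contrast, a both-or-either rule or a multiplicity adjustment.

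**The concern.** With two primary scores and 0.05 applied to each, the overall error rate depends on a rule that the plan does not state. If a significant result on either subscale would support the primary claim, the trial has two chances at 5% while it is sized and reported as if it had one. If both must succeed, the error is controlled, but the stated power no longer describes the chance of meeting the primary objective. On either reading, one of the plan's two headline operating characteristics is wrong.

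The missing contrast adds to this. Of the two terms named, the time effect does not compare the arms. A significant time-group interaction shows that the arms' profiles differ, not that ADM is higher. Without a named contrast and rule, which subscale and which comparison carry the conclusion could be settled after the data are seen.

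**Working it through.** **Inputs from the documents.** Difference 10, SD 20, alpha 0.05, power 85%, 72 per arm (section iib-10). Two primary scores, a baseline and three later assessments, p <= 0.05 in all analyses (section 9c i).

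**Assumed.** Two-sided tests, since sidedness is not stated. The documents give no correlation between subscales or between visits, so I use 0 to 0.8 between subscales and 0 to 0.7 between visits.

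**1. The plan's own figure.** n = 2[SD(z0.975 + z0.85)/difference]² = 2[20(1.960 + 1.036)/10]² = 71.8, or 72 per arm. It reproduces. A one-sided test would give 58. Section iib-10 also quotes a beta error of 0.1, but 90% power would need 85 per arm, so 72 agrees only with the 85%. Working back, the expected test statistic is 10/(20√(2/72)) = 3.00, and power is Φ(3.00 − 1.96) = 85.1% (84.6% by noncentral t). This is one comparison, with no allowance for a second.

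**2. Either subscale suffices.** If independent, the error is 1 − 0.95² = 9.75%. Simulating correlated normal test statistics gives:

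| Correlation between subscales | Chance of at least one false positive |
|---|---|
| 0.3 | 9.6% |
| 0.5 | 9.0% |
| 0.7 | 8.4% |
| 0.8 | 7.8% |

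If each subscale is instead judged by one overall time-group interaction test (3 degrees of freedom), the range is almost the same: 9.7% at correlation 0 to 7.9% at 0.8. The result therefore does not need visit-by-visit testing. Counting only false claims in favour of ADM, the figures are about half, roughly 4-5% against a nominal 2.5%.

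**3. Both subscales must succeed.** A false claim then requires at least one truly null subscale to cross 0.05, so the error cannot exceed 5%. With a true 10-point difference on both, power for both is 0.851² = 72% if independent and about 76% at a correlation of 0.5.

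**4. Six separate tests, any one sufficient.** If independent, 1 − 0.95⁶ = 26.5%. With both correlations at 0.5 it is about 22%. With 0.8 between subscales and 0.7 between visits it is about 17%.

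**5. Cost of control.** At alpha 0.025, z = 2.241 and power at 72 per arm is Φ(3.00 − 2.241) = 77.6% (76.8% by noncentral t). Restoring 85% at that level would take 86 per arm. Under Holm, with a 10-point effect on both subscales and a correlation of 0.5, power per subscale is about 82%, because the second test is made at 0.05 once the first has succeeded.

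**The case against.** The strongest reply is that the plan does not test each visit separately. It specifies a repeated measures analysis, which can give one overall interaction test per subscale. The hypothesis in the Specific Aims also asks for superiority at every visit, and an all-visits requirement does not inflate the error over time. This stands against a stronger reading that a reader might infer: that six comparisons are each tested at 0.05, so that the error is 26%, or that the claim could rest on the 2-week score alone. Section 9c i) specifies no such tests. The 26% also needs zero correlation between scores from the same patients, which is implausible. The loose statement that means will be compared leaves visit-level comparisons possible, but that is ambiguity rather than a plan for six tests.

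The reply does not remove the two-subscale problem. The hypothesis is not written as a decision rule, section 9c i) does not carry it into the test, and it does not settle whether both subscales must succeed. A global Breast Q score appears elsewhere in the document, but as the effectiveness measure for the cost-effectiveness analysis. The primary analysis uses the two domain scores.

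It is also fair to say that the 8-10% is conditional. The plan does not say that either subscale suffices, and under a both-must-succeed rule there is no inflation.

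**Conclusion.** The concern holds for the two subscales. If either counts as success, two-sided familywise error is about 8-10% rather than 5%, for assumed correlations between subscales from 0 to 0.8. If both must succeed, the 5% holds, but power for the primary objective is about 76% at a correlation of 0.5, against the stated 85%. The plan does not choose between these, and the sample size fits neither.

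The concern does not extend to the visits as a further source of stated error: 26% is the limit for six independent tests that the plan does not describe. Nor do the documents require 1 year to be the sole primary visit; the stated objective covers all three.

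**What to change.** In section 9c i), before any comparison of Breast Q scores by arm:

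- Name one between-arm contrast from the planned repeated measures model, the same for each subscale. The 1-year difference is one option. It would narrow the objective in the Specific Aims, so the choice is the sponsor's.
- State the rule for the two subscales. One choice is Holm's procedure: the smaller p-value against 0.025 and, if that succeeds, the other against 0.05. The alternative is a fixed order, with the second subscale tested only if the first succeeds.
- Describe the individual visit comparisons as supportive.
- If the intention is that both subscales must succeed, say so, keep 0.05 for each, and restate the power in section iib-10 for that rule.

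This costs a paragraph of text and needs no new data. The price of Holm is power: about 77% at 72 per arm if only one subscale is affected, and about 82% per subscale if both have a 10-point effect. A fixed order keeps 0.05 and the stated 85% for the first subscale, but the second then depends on the first. Baseline adjustment may recover some power: at an assumed correlation of 0.5 with baseline, power at alpha 0.025 would be about 88%. The documents give no such correlation, and section iib-8 uses a pre-operative module at baseline and a post-operative module afterwards, so that recovery should not be counted on.
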